8.2. Study Duration

After discontinuation of study treatment, all patients will be followed for survival every 4 weeks until death or until the target number of events (deaths) is met, unless the patient has withdrawn consent from the trial. Patients may request discontinuation of study treatment but agree to survival follow-up (this is not considered withdrawal of consent from the trial).

The final analysis will be performed once 384 events (deaths) are reached. If the primary endpoint of the study is met and efficacy as well as safety support a favorable benefit/risk ratio

for TAS-102, patients currently or previously treated with placebo who continue to meet study eligibility criteria will be offered the option to crossover to open-label TAS-102. Patients who are currently receiving TAS-102 will also be switched to open-label TAS-102 at that time.

Patients who receive open-label TAS-102 treatment after conclusion of survival follow-up will be followed for safety and tumor response according to the site standard of care (see Section 9.3). The end of study is defined as completion of safety follow-up for the last patient who discontinues study treatment, including patients who receive open-label TAS-102.

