8.6. Discontinuation from Study Follow-up

As described in Section 10.1.13, patients who discontinue study treatment for reasons other than radiologic disease progression (eg, intolerable side effects) should continue to be followed for tumor response every 8 weeks until the patient develops radiologic disease progression (or death) or initiation of new anticancer therapy (whichever occurs first).

All treated patients will be followed for survival every 4 weeks until death, or until the target number of events is reached (whichever is sooner), unless the patient has withdrawn consent from the trial. Patients may request discontinuation of study treatment but agree to survival follow-up (this is not considered withdrawal of consent from the trial). The Investigator should make every effort to contact the patient or primary caregiver to determine his/her survival status. Times and dates of contact must be documented in the patient's records.

A patient will be considered "Discontinued from Study Follow-up" when one of the following occurs:

- Patient dies
- Target number of events (384 events) is reached and final analysis performed
- Study is stopped based on Data Monitoring Committee (DMC) recommendation
- Study is terminated by the Sponsor or Regulatory Agencies

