10.1.13. Tumor Measurements

Computed tomography tumor assessments/imaging studies of the chest and abdomen (and pelvis if clinically indicated) must be obtained at each time point listed below for all patients:

- Within 28 days prior to Day 1 of Cycle 1. Scans obtained prior to patient ICF may be used if the date of the scan is within 28 days of randomization.
- Every 8 weeks during study treatment
- For patients who discontinue treatment for reasons other than radiologic disease progression, every effort should be made to perform a tumor assessment prior to the start of new anticancer therapy.
- For patients who discontinued treatment for reasons other than radiologic disease progression, every 8 weeks until the patient develops radiologic progression or the start of new anticancer treatment (whichever occurs first)

On-site tumor assessments will be performed by the Investigator/local radiologist according to RECIST criteria (version 1.1, 2009). Results of these assessments including response for target and non-target lesions and appearance of new lesions will be the basis for the continuation or discontinuation of study medication. Response definitions are provided in Section 11.

If the Investigator determines that a patient develops clinical progression manifested by symptomatic deterioration but not supported by radiologic evidence of progression, the patient should stop treatment. Symptoms of clinical progression must be documented in the patient's source documents. Every effort should be made to document objective progression even after discontinuation of treatment.

If a patient is withdrawn due to radiologic disease progression, additional CT scans are not required at the end of treatment.

The same method of assessment and the same technique must be used to characterize each identified and reported lesion at Baseline, throughout the study, and during the follow-up period.

All patients' files and radiological assessments must be available for source verification. Results of any unscheduled evaluations should be recorded in the patient's source documents.

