10.2.8. Survival Follow-up after 30-Day Safety Visit

The following assessments should be obtained at scheduled 4-week (± 7 days) time intervals during the survival follow-up period:

- Tumor measurement (by CT scan, see Section 11) every 8 weeks until radiologic disease progression (for patients who discontinued treatment for reasons other than disease progression) or initiation of new anticancer therapy (whichever occurs first)
- Concomitant medications collect antitumor therapies only
- Contact patient/caregiver to determine survival status (alive/dead)
- SAE collection only if the SAE is related to study medication

Patients will be followed for survival until the target number of events is reached. The Investigators will be informed when this target is reached.

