3.2. Study Endpoints

3.2.1. Primary Efficacy Endpoint

Overall survival (OS) is the primary efficacy endpoint of this study and is defined as the time from the date of randomization to the death date (ITT population). In the absence of death confirmation or for patients alive as of the OS cut-off date, survival time will be censored at the date of last study follow-up, or the cutoff date, whichever is earlier. The cut-off date will be defined by the date of the 384th death. Patients having a documented survival status (alive or dead) after this date will be censored at the cut-off date.

With the OS cut-off date being event driven, for operational efficiency, the cut-off date for all other study endpoints will be fixed at close proximity of the OS cut-off date, when the milestone is nearing completion.

The clinical cut-off date for all endpoints other than OS was fixed as 31st of March 2018. Details of the rules for cut-off of the submission database are provided in the **CCI**

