4.5.5. Quality of Life

Analysis of the quality of life will be performed using EORTC Quality of Life Questionnaire - Core Questionnaire (EORTC QLQ-C30) and Gastric-specific module (QLQ-STO22). The EORTC QLQ-C30 was developed as an integrated system for assessing the health related quality of life (QoL) of cancer patients participating in international clinical trials. It is composed of both multi-item scales and single-item measures. These include five functional scales, three symptom scales, a global health status / QoL scale, and six single items. Each of the multi-item scales includes a different set of items - no item occurs in more than one scale.

Patients will complete the EORTC QLQ-C30QLQ-STO22 CCI at the following time points:

- Within 7 days prior to randomization
- Prior to dose administration on Day 1 of Cycles ≥ 2 At the 30-day Safety Follow-up Visit if not performed within the previous 4 weeks

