8.6. End of Study

The final data cut off will be defined by the date of the 384th death. All patients dying on the calendar date of the 384th death will be included in the analysis should more than one patient die on the calendar date of the 384th death. Subjects that will be alive on the calendar date of the 384th death will be considered as ongoing study.

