10.4.4.4.6. Time to Deterioration – Main Analysis

Time to first deterioration in QoL (refer to [Section 10.4.4.4.5](#) for definition) will be evaluated for each arm using Kaplan-Meier estimates and compared using the log-rank test (and Cox proportional hazards models adjusting for the baseline value of the EORTC QLQ-C30 and QLQ-STO22 score, country and primary tumour type). Patients with no deterioration in EORTC QLQ-C30 and QLQ-STO22 scores will be censored at the end of study, cut-off date or death date.

CCI

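### Time to QoL deterioration is censored at death, cut-off or end of study instead of the last questionnaire, so unmeasured time counts as deterioration-free and can only raise the curves

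*SAP*

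**What the plan says.** The main-analysis rule in SAP 10.4.4.4.6 is: "Patients with no deterioration in EORTC QLQ-C30 and QLQ-STO22 scores will be censored at the end of study, cut-off date or death date". It does not say which of the three dates applies when they differ. Arms are compared by Kaplan-Meier curves, a log-rank test and Cox models. The event, defined in SAP 10.4.4.4.5, is a fall of at least five points from baseline, so it cannot be recorded without a completed questionnaire.

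Questionnaires are due within 7 days before randomization, before dosing on Day 1 of each cycle from Cycle 2, and finally "At the 30-day Safety Follow-up Visit if not performed within the previous 4 weeks" (SAP 4.5.5; Protocol 10.1.12 agrees). After that, Protocol 10.2.8 lists tumor scans where applicable, antitumor therapy, related SAEs and survival status ("Contact patient/caregiver to determine survival status (alive/dead"), but no QoL. The survival follow-up column of both study schedules has no QoL entry either.

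The SAP treats similar endpoints differently. Time to ECOG deterioration, also measured no later than the 30-day visit, is censored at the last ECOG assessment (SAP 3.2.3.3 and 10.4.4.3). PFS for patients alive without progression is censored at the last tumor assessment (SAP 3.2.2). The visible text gives no reason for handling QoL otherwise.

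**The concern.** Between the last questionnaire and death or cut-off, deterioration cannot be observed, yet the patient is counted as at risk and not deteriorated. This overstates how long QoL is preserved in both arms. It can also distort the comparison: if one arm stops treatment earlier, it collects more unmeasured time and looks better.

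Stopping is unlikely to be unrelated to QoL. Protocol 10.1.13 says that in case of "clinical progression manifested by symptomatic deterioration but not supported by radiologic evidence of progression, the patient should stop treatment". Measurement can therefore end just as the patient worsens.

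The stake is limited to an other-secondary endpoint. The QLQ-C30 has 5 + 3 + 1 + 6 = 15 scores and the QLQ-STO22 has 5 + 4 = 9 (SAP 10.4.4.4), so 24 scores are tested at a nominal 0.05. PFS is the only key secondary endpoint for registration (SAP 10.3). OS, PFS, the 384-death target, and the descriptive and week 4/8/12 QoL analyses do not depend on this rule.

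**Working it through.** The plan gives no figure for this endpoint, so there is none to reproduce.

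**Step 1: can any of the three dates coincide with the last questionnaire?** Death and cut-off fall on or after the last counted QoL. End of study is not clearly defined at patient level, but its visible definitions also fall late:
- SAP 8.6, under its End of Study heading: "The final data cut off will be defined by the date of the 384th death".
- Protocol 8.2: "The end of study is defined as completion of safety follow-up for the last patient who discontinues study treatment".
- Protocol 8.6, among the patient-level events ending follow-up: "Target number of events (384 events) is reached and final analysis performed".

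**Step 2: direction.** The estimate is S(t) = ∏(1 − d_j/n_j) over event times up to t. With QoL after the cut-off excluded under both rules, event times and d_j are identical. Each patient without an event is censored no earlier under the written rule, so every n_j is at least as large, every factor is at least as large, and S_written(t) ≥ S_last(t) at every t, in each arm. Numerical checks found no violation in 5,000 random datasets, nor in 500 simulated samples of 167 patients.

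**Step 3: size, illustrative only.**
- From the documents: control OS median 5 months and HR 0.70, so 5/0.70 = 7.14 months on TAS-102; 18 months' accrual plus 8 months (Protocol 13.4); 500 patients at 2:1, about 333 v 167; QoL every 28 days on treatment plus the 30-day visit.
- Assumed: exponential times; median time on TAS-102 of 2.9 months (borrowed from the Phase 2 median PFS in Protocol 6.1.2.2); placebo 2.9, 2.3, 1.8 or 1.5 months; deterioration median 3 or 6 months in both arms, so the true 6-month value is 0.5^(6/3) = 0.25 or 0.5^(6/6) = 0.50; Gaussian-copula correlation 0, 0.3 or 0.5 among deterioration, stopping and death.

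Kaplan-Meier estimate at 6 months, range over arms and durations:

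| True value | Correlation | Written rule | Last-QoL censoring |
|---|---|---|---|
| 0.25 | 0 | 0.45–0.55 | 0.20–0.24 |
| 0.25 | 0.3 | 0.47–0.56 | 0.31–0.33 |
| 0.25 | 0.5 | 0.47–0.59 | 0.36–0.39 |
| 0.50 | 0 | 0.66–0.73 | 0.44–0.49 |
| 0.50 | 0.3 | 0.70–0.77 | 0.59–0.60 |
| 0.50 | 0.5 | 0.73–0.81 | 0.65–0.69 |

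The gap between the rules grows with time: about 0.00–0.01 at week 4, 0.01–0.06 at week 8, 0.02–0.13 at week 12 and 0.07–0.34 at 6 months.

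**Step 4: between-arm comparison with no true QoL difference (HR 1.0, TAS-102 v placebo).** Rejection is by a two-sided nominal 5% log-rank test, 333 v 167 patients.

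| Placebo treatment median (months) | Correlation | HR, written | HR, last QoL | Rejection, written | Rejection, last QoL |
|---|---|---|---|---|---|
| 2.9 (equal) | 0 | 1.00 | 0.99 | 4–5% | 5% |
| 2.9 (equal) | 0.5 | 1.04 | 1.06–1.07 | 5–6% | 7% |
| 1.5–2.3 | 0 | 1.08–1.29 | 0.92–0.98 | 15–17% at 1.8; 25–29% at 1.5 | 7% at 1.8; 7–9% at 1.5 |
| 1.5–2.3 | 0.5 | 1.15–1.56 | 1.07–1.14 | 32–41% at 1.8; 50–67% at 1.5 | 7–8% at 1.8; 7% at 1.5 |

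Under the written rule, the excess rejection with unequal durations favours placebo.

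**The case against.** Five points deserve an answer.

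- **The 6-month figures show the effect at its largest.** The protocol limits its representative QoL time points to Cycles 2 to 4 because of expected compliance and treatment duration, and the gap between the rules is small there. This stands as a qualification of size. The Kaplan-Meier curves and log-rank test are not limited to those weeks, however.
- **The magnitudes rest on assumptions.** This is true. The highest rejection rates need both the widest duration gap and the strongest correlation. With equal durations the written rule holds its 5% level approximately. Only the ordering of the curves is established without assumptions.
- **End of study might mean the 30-day visit.** Both schedules have a column heading that joins end of treatment and end of study. That heading also covers survival follow-up, so it does not move censoring back to the last QoL.
- **Redacted text follows SAP 10.4.4.4.6.** It may contain analyses with other censoring. The visible rule is labelled the main analysis, and a redacted sensitivity analysis would not change it.
- **Last-assessment censoring is also imperfect.** This stands. At correlation 0.5 it leaves about 40–70% of the curve inflation, and with equal durations it gains nothing on the hazard ratio. With independent stopping and unequal durations it leans towards TAS-102 (0.92–0.98).

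**Conclusion.** The concern holds. The rule counts time without QoL measurement as deterioration-free and can only raise each arm's curve relative to last-assessment censoring. In the assumed scenarios the 6-month excess over that rule is about 0.07 to 0.34. Last-assessment censoring was closer to the true curve in every one, without always reaching it.

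The effect on the comparison is conditional. It is negligible to small if time on treatment is equal, and works against the arm observed longer if it is not. The documents do not say which applies. Because the endpoint is other-secondary and the primary and key secondary results are untouched, this should be corrected but is not critical to the trial's conclusion.

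**What to change.** In SAP 10.4.4.4.6, for each score, censor patients without deterioration at the last evaluable assessment of that score on or before the cut-off for non-OS endpoints (SAP 3.2.1: "The clinical cut-off date for all endpoints other than OS was fixed as 31st of March 2018"). Censor at randomization if there is no post-baseline assessment, and say how patients without a baseline score are handled.

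Unless the redacted text already provides them:
- keep the present rule as a sensitivity analysis, stating which of the three dates applies;
- add an analysis counting death as an event, labelled a composite. It carries the OS effect: with an OS hazard ratio of 0.70 and no QoL difference, it gave 0.82–0.94 in these scenarios.

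The cost is SAP wording and one programming change, made before unblinding as SAP section 2 requires of analysis decisions. Nominal follow-up will be shorter. The SAP should state that bias is reduced, not removed: the hazard ratio may lean slightly towards TAS-102 if stopping is independent of deterioration and durations differ, or against it (1.06–1.14 in the simulations at correlation 0.5) if patients stop because they deteriorate.

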11. SAFETY ANALYSES

This Section contains instructions how the analysis of the safety aspects of the collected data will be performed and presented. As a general rule (unless otherwise is stated) efficacy analysis will use values of stratification factors collected on CRF pages.

11.1. Adverse Events

11.1.1. Definition of Adverse Event

An *adverse event* (AE) is defined as any untoward medical occurrence in a clinical investigation of a patient that may or may not have casual relationship with treatment (21 CFR 312.32(a)). An AE can therefore be any unfavorable and unintended sign (including a clinically significant abnormal laboratory finding), symptom, or disease temporally associated with the clinical study, independent of the relationship to the investigational product.

Any AE that started after signing of informed consent and before treatment start date will be presented in the Medical History section of the summary tables.

Any adverse event starting more than 30 days after the last dose of study medication will be excluded from the summary analyses, unless the event caused patient discontinuation from the study.

11.1.2. Definition of Treatment Emergent Adverse Event

Treatment-emergent adverse events (TEAE) will be defined as those events, which meet one of the two criteria:

- started on or after treatment start date (first dose of study medication ⇔ Cycle1, Day 1) through 30 days after treatment end date (last dose of study medication)
- started before treatment start date and became worse (more severe) after treatment start date (first dose of study medication ⇔ Cycle1, Day 1) through 30 days after treatment end date (last dose of study medication)

Only treatment-emergent adverse events will be summarized, non-treatment emergent AE will be listed only.

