10.1.15. Adverse Event Assessment

Any untoward medical events (AEs or SAEs) that occur from the first dose of study medication (Day 1, Cycle 1) through 30 days after last dose of study medication should be recorded in the AE section of the eCRF. Any AEs/SAEs that occur from the time of signed informed consent until the first dose of study drug should be reported on the Medical History section of the eCRF.

SAEs should be reported to Taiho Pharmacovigilance or designee. If any medical occurrences **outside** the 30-day follow-up period are reported to or observed by the Investigator that he/she believes are related to the administration of the study medication, it is the Investigator's responsibility to record those events on the eCRF and, if any of those events are serious, then the Investigator has to report this occurrence to Taiho Pharmacovigilance or designee. See Section 12.1.1 and Section 12.1.2, respectively, for definitions and detailed reporting of AEs and SAEs.

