12. REPORTING SAFETY INFORMATION

12.1. Adverse Events/Serious Adverse Events

12.1.1. Adverse Events

An **adverse event** (AE) is any untoward medical condition that occurs in a patient while participating in a clinical study and does not necessarily have a causal relationship with the use of the study medication.

Treatment emergent AEs are AEs that occur from the initiation of any study treatment administration, and do not necessarily have a causal relationship to the use of the study treatment.

Provide a complete and specific clinical diagnosis as an AE verbatim term. If a diagnosis is not available, then report signs and symptoms. The Common Terminology Criteria for Adverse Events (CTCAE Version 4.03) terms are to be used to assess severity/provide the grade for each AE that is reported.

Refer to Section 12.1.5, Section 12.1.6, and Section 12.1.7 for definitions and reporting of pregnancy, medication errors, and overdose, respectively.

Any untoward medical event that occurs outside the period of patient follow-up (30 days after the last dose of study treatment or until the start of new antitumor therapy, whichever is earlier) is not considered an AE unless determined by the Investigator to have a causal relationship with the study treatment.

If any SAEs are observed after the patient follow-up period has ended, only those SAEs determined to have a causal relationship with the study medication will be recorded in the case report form.

Symptoms or laboratory or instrumental (eg, electrocardiographic) abnormalities of a pre-existing disease, such as cancer or other disease, should not be considered an AE. However, occurrences of new symptoms as well as worsening of pre-existing medical conditions are considered AEs. In addition, a new laboratory or instrumental abnormality that has a clinical impact on a patient (eg, resulting in study medication dose reduction, treatment delay, treatment discontinuation, requires treatment due to abnormal values, or is considered medically important by the Investigator) is considered an AE, unless it is considered part of clinical manifestations to a clinical diagnosis that is already reported as an AE.

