13.3.3. Safety Analyses

The safety evaluations will focus on AEs and laboratory assessments. All patients included in the AT Population will be evaluated by treatment arm in the safety analysis.

Adverse events will be coded according to the Medical Dictionary for Regulatory Activities (MedDRA) terminology and the severity of the toxicities will be graded according to the NCI CTCAE criteria, v4.03, where applicable. Concomitant medications will be coded according to the World Health Organization Drug Dictionary (WHODD). Hematological and chemistry laboratory parameters will be graded according to the NCI CTCAE v.4.03 criteria, where applicable.

All AEs will be summarized (incidence) and listed by the System Organ Class (SOC), preferred term (PT), toxicity/severity grade, and causal relationship to study medication. In addition, separate summaries of SAEs and Grade 3 and 4 AEs will be presented.

Absolute values and changes from baseline for hematology and serum chemistry parameters will be summarized by cycle. In addition, worst severity grade, and time to event will also be summarized.

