11.2.1. Overview and Summaries of Adverse Events

AE incidence will be calculated by the worst CTCAE grade at every level of summarization (SOC or PT), i.e., if a patient has multiple occurrences of the same AE with different toxicity grades during a period, the patient will be accounted for in AE frequency tabulation in the worst grade. An overall summary table (overview) of all adverse events will be presented, summarizing:

- Total number of TEAE
- Total number of Serious TEAE
- Total number of TEAESI
- Total number and percentage of subjects with at least one TEAE
- Total number and percentage of subjects with at least one Serious TEAE
- Total number and percentage of subjects with at least one related TEAE
- Total number and percentage of subjects with at least one related Serious TEAE
- Total number and percentage of subjects with at least one severe (Grades 3 - 5) TEAE
- Total number and percentage of subjects with at least one TEAE leading to dose modification
- Total number and percentage of subjects with at least one TEAE leading to dose reduction
- Total number and percentage of subjects with at least one TEAE leading to discontinuation of the study treatment
- Total number and percentage of subjects with at least one TEAE leading to death
- Total number and percentage of subjects with at least one TEAESI

The primary AE summary will also be all TEAE by SOC and PT regard to the relationship to study medication (AT population CCI).

In addition to the overview table, a number of the summaries will be created. The primary AE summary will tabulate all TEAE by SOC and PT (AT population CCI - Section 4.1). Other summaries will present various aspects of collected AE. Calculations in the tables will follow the basic principles of counting described in the beginning of Section 11.2. The following summaries will be created:

- TEAE (all and grades 3-5) summarized by SOC and PT, by treatment group (AT population CCI)
- TEAEs (all and grades 3-5) related to study drug summarized by SOC and PT, by treatment group (AT population CCI)
- TEAE summarized by SOC and PT, by CTCAE grades, by treatment group (AT population)
- TEAE (all and grades 3-5) summarized by PT in descending order, by treatment group (AT population)
- TEAE (all and grades 3-5) related to study drug summarized by PT in descending order, by treatment group (AT population)
- TEAE (all and grades 3-5) leading to dose modification summarized by SOC and PT, by treatment group (AT population)

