- TEAE (all and grades 3-5) leading to dose reduction summarized by SOC and PT, by treatment group (AT population)
- TEAE (all and grades 3-5) leading to treatment discontinuation summarized by SOC and PT, by treatment group (AT population)
- TEAE (all and grades 3-5) leading to death summarized by SOC and PT, by treatment group (AT population)
- TEAE of Special Interest (all and grades 3-5) summarized by SOC and PT, by treatment group (AT population CCI [REDACTED])
- Incidence rate (per 100 patient years) of all TEAESIs (summarizing the incidence rate (per patient year) for each SOC and PT as per description in [Section 8.9.](#))
- Serious TEAE (all and grades 3-5) summarized by SOC and PT, by treatment group (AT population CCI [REDACTED])
- Serious TEAE (all and grades 3-5) related to study drug summarized by SOC and PT, by treatment group (AT population CCI [REDACTED])
- Serious non-treatment emergent AE (all and grades 3-5) summarized by SOC and PT, by treatment group (AT population)
- Selected adverse events and lab abnormalities of special interest (the exact list will be determined prior to study unblinding) will be presented in the graphical form (“forest plot” format). Figure will include the relative risk and associated 95% asymptotic confidence intervals

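### The SAP's 30-day TEAE window has no exception for late drug-related events, so the related, serious-related and leading-to-death tables can omit adverse events that the protocol counts (minor)

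*SAP*

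**What the plan says.** **Protocol.** Section 12.1.1 says that an event after the follow-up period "is not considered an AE unless determined by the Investigator to have a causal relationship with the study treatment". Its description of treatment-emergent events starts at first treatment and gives no upper time limit. Section 10.1.15 makes it the investigator's "responsibility to record those events on the eCRF and, if any of those events are serious", also to report them to pharmacovigilance. During survival follow-up, section 10.2.8 limits routine capture: "SAE collection only if the SAE is related to study medication". Section 13.3.3 then states: "All AEs will be summarized (incidence) and listed by the System Organ Class (SOC), preferred term (PT), toxicity/severity grade, and causal relationship".

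**SAP.** Section 11.1.2 runs the treatment-emergent period "through 30 days after treatment end date (last dose of study medication", whatever the causality, and adds: "Only treatment-emergent adverse events will be summarized, non-treatment emergent AE will be listed only". Section 11.1.1 drops events starting more than 30 days after last dose from the summaries, unless the event made the patient leave the study. Section 11.2.1 builds the attribution tables on TEAEs: "TEAEs (all and grades 3-5) related to study drug summarized by SOC and PT, by treatment group" and "Serious TEAE (all and grades 3-5) related to study drug summarized by SOC and PT, by treatment group". The leading-to-death table is likewise a TEAE table. The same section also lists a by-arm table of serious events that are not treatment-emergent.

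**The concern.** The protocol keeps late events in scope for one reason: the investigator has attributed them to the drug. The SAP then leaves those events out of the tables a reader consults for attributed harm. The by-arm counts of related, serious-related and fatal adverse events could therefore be lower than the protocol's own definition of an adverse event implies, and nothing in those tables would say so. For drug-related death, a single event matters.

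The dosing rules give a concrete route into the gap. A patient held for toxicity can go more than 30 days after the last dose while the decision to stop permanently is still open (Protocol 8.5 and 9.2.4.4).

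**Working it through.** **1. Tracing a related event that starts more than 30 days after last dose**

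| Type of event | Protocol status | Related table | Serious-related table | Leading-to-death table | Where the readable SAP shows it |
|---|---|---|---|---|---|
| Non-serious | An AE; recorded if reported to or seen by the investigator | No | Not applicable | Not applicable | Listing only |
| Serious, not fatal | An AE; collected in survival follow-up | No | No | Not applicable | Serious non-TEAE table, no causality split |
| Serious, fatal | An AE; collected in survival follow-up | No | No | No | Serious non-TEAE table, not separated from other grades 3-5 |

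The three entries in the fatal row change only if the 11.1.1 exception is read to override the TEAE restriction. An event that starts inside the window and proves fatal later is not affected, because the window is applied to onset.

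**2. The two wording conflicts**
- SAP 11.1.2 says that events outside the window are not summarised. SAP 11.2.1 nevertheless tabulates the serious ones.
- SAP 11.1.1 keeps late events that caused the patient to leave the study. Protocol 8.6 lists death among the ways study follow-up ends, so a fatal late event may qualify. The SAP does not say whether it does, and 11.1.2 and the table titles still require a TEAE.

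**3. How the gap can be reached**
- Last dose of a full cycle: Day 12 (Protocol 9.2.1). The window closes on Day 12 + 30 = Day 42.
- Next cycle due on Day 29, with a delay of at most 28 days (Protocol 9.2.4.4): Day 29 + 28 = Day 57, which is 57 - 12 = 45 days after last dose.
- If the patient is never re-dosed, a related event starting on Days 43 to 57 is not a TEAE. A re-dosed patient is not affected. The documents give no frequency for this.

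**4. Scale**

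No figure in the plan can be reproduced here, and no rate of late related events is given. The following only sets bounds.
- Assume 500 × 2/3 = 333 treated TAS-102 patients. Exact (Clopper-Pearson) 95% intervals: 0/333 = 0% (0 to 1.10%); 1/333 = 0.30% (0.01 to 1.66%).
- To see who could have a late event, assume exponential survival with a TAS-102 median of 5/0.70 = 7.1 months, from the design values. The death hazard is d = ln 2/(5/0.70) = 0.0970 per month.
- Assume median time on treatment of 1.5, 2.0 or 2.9 months. The value 2.9 is the Phase 2 median PFS (Protocol 6.1.2.2), used as a stand-in; the other two are assumptions. The total hazard of leaving treatment is t = ln 2/median = 0.4621, 0.3466 or 0.2390. The window is w = 30/30.44 months.
- P(alive past the window) = ((t - d)/t) × exp(-d·w) = 0.718, 0.654 or 0.540, that is 239, 218 or 180 of 333. This is the number who could have such an event, not the number who do.

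**5. Why the rates should stay at 30 days**
- Mean time inside the window = 1/t + ((t - d)/t) × (1 - exp(-d·w))/d = 2.91, 3.56 or 4.74 months. Multiplied by 333/12, this gives 80.7, 98.8 or 131.6 patient-years.
- One late event added to a numerator without its person-time would raise a rare-event rate by 100/80.7 = 1.24, 100/98.8 = 1.01 or 100/131.6 = 0.76 per 100 patient-years. SAP 8.9 time at risk stops at the end of the TEAE period, so late events do not belong in those rates.

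**The case against.** The case on the other side is substantial.

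- **The serious non-TEAE table already shows most of what matters.** Events before first dose go to medical history, and after the window only related events are recorded. In practice this table would hold mainly late related serious events, by arm, and a fatal event is serious by definition. This stands. A reader might infer that the plan makes late drug-related deaths vanish from every summary; the documents do not support that. What remains is that the table states neither causality nor fatal outcome, and that 11.1.2 as worded rules it out.
- **The 11.1.1 exception may keep fatal events in the summaries.** That reading is open. The SAP does not settle it, so the leading-to-death part of this point is the least certain.
- **A 30-day window is conventional and follows the protocol's main reporting period.** Agreed. A reader might infer that the window itself is wrong; it is not. The fault is the missing provision for events that the protocol deliberately keeps in scope beyond it.
- **Late non-serious events are captured only when they happen to be reported.** This also stands. An incidence built on them is hard to interpret and should not be pooled with in-window counts. That argues for showing them separately. It does not explain leaving them out of every summary when Protocol 13.3.3 says all adverse events are summarised.
- **Redaction.** SAP 11.2.2 and the Data Handling Guidance are blacked out, and the related and serious-related rows run into redacted text. Another output may exist. The point covers the readable text only.

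**Conclusion.** The point holds, as a minor one. On the readable text, SAP 11.1.2 and 11.2.1 are narrower than Protocol 12.1.1, 10.1.15 and 13.3.3. Late events judged related are outside the related and serious-related tables, and outside the leading-to-death table unless 11.1.1 is read to rescue fatal ones. Late related serious events still appear by arm in the serious non-TEAE table. Late related non-serious events appear in no readable summary.

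The size cannot be stated. The 0/333 against 1/333 comparison shows what one event would do. The 54% to 72% of patients alive past the window rests on the exponential model and the assumed treatment durations. A reader might take that share as a measure of under-reporting; it only describes who could be affected. The number of events is probably small. They are still recorded and listed, and no efficacy result, alpha level or power figure is touched.

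**What to change.** 1. In the related, serious-related and leading-to-death incidence tables, add a separate row or a footnote for adverse events starting more than 30 days after last dose that the investigator judges related. State there that only related events are ascertained after 30 days, so the late counts are not comparable with the in-window ones.
2. Leave the 30-day TEAE definition in place for time at risk in SAP 8.9 and for every rate per 100 patient-years.
3. In SAP 11.1.2, name the serious non-TEAE table as an exception to the listing-only rule.
4. In SAP 11.1.1, say whether death counts as leaving the study for the purpose of that exception.

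The cost is a few sentences in two SAP sections, one derived flag, and a row or footnote in three table types. Onset date and causality are already collected, so nothing new is needed from sites. The one drawback, related-only ascertainment after 30 days, is met by keeping the late events apart.
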